#### **5.2.4.d. Incorporating Limited Data on Methadone Maintenance Therapy (MMT)**

We will describe the availability of MMT by health system. For health systems with methadone maintenance outpatient treatment programs (OTPs) data available (one HCS and possibly a second), we will incorporate procedure codes for Methadone Maintenance OTPs when estimating the objective 1 main implementation outcome in this analysis. Based on consultation with addiction medicine specialists, we will require at least 2 procedure codes to be included as using Methadone Maintenance from an OTP and assume that treatment lasts for the time period between codes for a maximum of 365 days per code (e.g., 2 codes 365 days apart). The end date of MMT (i.e., last claim) will be estimated at half the average days between previous MMT codes.

#### **5.2.4.e. Combined Sensitivity Analysis Using All Optimal Data**

We will conduct a sensitivity analysis of the objective 1 main implementation outcome using both MMT data (1-2 health systems) and dispensing data as they are detailed above. This will be done across the 1-2 health systems that have both MMT and dispensing data.

### **5.2.5 Timing of OUD Diagnosis**

Our primary analysis includes all days of OUD treatment for buprenorphine and injectable naltrexone, including among patients with and without an OUD diagnosis prior to randomization, and among patients who were seen in the clinic previously as well as patients who were new to the clinic or to the health system entirely. If we find that the PROUD intervention increases the provision of OUD treatment based on our primary analysis, we will further explore which of the following mechanisms may have contributed to this increase: (1) by increasing the number of days treated among individuals in the clinic pre-randomization who also had a documented OUD diagnosis pre-randomization, (2) by increasing the number of days treated among individuals in the clinic pre-randomization but who did not have a documented OUD diagnosis pre-randomization, or (3) by attracting patients post-randomization not previously seen in the clinic who have OUD (from within or outside the HCS; Supplemental Figure Shell 1, Objective 2, Section 10.2). To address each of these possibilities, we plan to conduct secondary analyses of the Objective 1 outcome among each of these 3 subsets overall by arm (as well as conducting descriptive analyses by health system). To facilitate comparison of days treated across these different study populations, we will apply the same scaling factor as in the definition of the primary analysis of the outcome (i.e., the number of patient-days of OUD treatment will be divided by the total number of patients seen in the clinic over the follow-up period).

### **5.2.6 Secondary Analyses Among Patients Treated for OUD**

Our primary outcome is a scaled clinic-level measure of OUD treatment among all patients assigned to the clinic, scaled by the number of patients seen in the clinic, over the 2-year post-randomization period. In secondary analyses, we plan to repeat the primary analysis where we calculate the outcome measure among patients with documented OUD treatment during the 2 years post-randomization (and scale by the number of patients with OUD; see Table Shell 6, Objective 1, Section 10.1). However, we note that because the intervention could impact both the

denominator (number of patients diagnosed with OUD) as well as the numerator (initiation and duration of treatment among treated patients), interpretation of these secondary analyses should be interpreted cautiously.

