## 4.0 OUTCOME MEASURES

### 4.1 Definition of Primary Implementation Outcome Measure

The primary outcome (clinic-level measure) is the number of patient days of OUD medication treatment documented in the EHR in each clinic post-randomization. To account for varying clinic sizes, the clinic-level outcome is divided by the number of patients seen in the clinic post-randomization and then multiplied by an appropriate scaling factor in order to report the results (e.g., multiplying by 10,000 to calculate the number of patient days of OUD treatment per 10,000 patients), and reported as patient-years of treatment provided by a clinic (calculated by simply dividing days of OUD treatment by 365).

“OUD medication treatment” includes medications for OUD that can be prescribed in PC and documented in EHRs—buprenorphine formulations indicated for OUD (oral, implants, sustained release injection with or without an OUD diagnosis) or injectable extended release (XR) naltrexone with a diagnosis of OUD. An OUD diagnosis is required for injectable XR naltrexone because it is often used for alcohol use disorders (AUD). We do not require an OUD diagnosis for buprenorphine because there are buprenorphine formulations specific for OUD and PROUD Phase 1 analyses revealed OUD diagnoses are often missing, consistent with the literature. Further, an OUD diagnosis is likely to be documented by PROUD clinic providers based on the PROUD NCM manual, so that requiring an OUD diagnosis could bias findings toward favoring the intervention clinics.

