**Table 7.** Clinic level primary and secondary implementation outcomes of the Primary Care Opioid Use Disorders Treatment (PROUD) trial among patients receiving OUD treatment during the 2 years post randomization.

Randomization:			
Scaled implementation measure among treated patients	6 intervention clinics	6 usual care clinics	P value a
	Mean (SD) across clinics per 100 patients treated in the clinic post randomization		
Patient years of OUD treatment b			
Primary outcome (ITT analysis) c			
Limited to the time period after the NCM started seeing patients d			
Limited to health systems that successfully implement the MA model e			
Number of patients with:			
Newly initiated treatment a, f			
On-going treatment a,g			
80% of days covered by OUD treatment			
Newly initiated treatment a, f			
On-going treatment a,g			
≥ 6-months retention in OUD treatment h			
Newly initiated treatment a,f			
On-going treatment a,g			
Discontinuation of OUD treatment i			
Newly initiated treatment a,f			
On-going treatment a,g			
Buprenorphine average daily dose in mg			
Buprenorphine daily dose ≥16 mg j			
Naloxone prescription			

a Random effects model adjusted for the primary outcome measure at baseline (two years prior to randomization)

b Defined as having a medication order or procedure code for buprenorphine formulations that are indicated for OUD or having a medication order or procedure code for XR-NTX and 2+ visits with diagnosis code for OUD or opioid overdose (diagnosis codes can be during the 2-years pre or 2-years post randomization)

c Includes all clinics and all follow-up time post randomization

d Time period during which NCM seeing patients: X days for clinic A, X days for clinic B, X days for clinic C, X days for clinic D, X days for clinic E, and X days for clinic F

e Successful implementation defined as the nurse care manager seeing at least 30 patients. Analysis includes X of 6 health systems.

f OUD treatment in the 2 years post randomization and no OUD treatment in the prior 365 days

g OUD treatment in post-randomization, but not meeting criteria for initiated

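### SAP 5.2.6 scales treated patients' days by the number of patients diagnosed with OUD, while its results shell scales by patients treated; the two rules define different endpoints and one must be chosen

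*SAP*

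**What the plan says.** SAP 5.2.6 (Secondary Analyses Among Patients Treated for OUD) will rerun the primary model but "calculate the outcome measure among patients with documented OUD treatment during the 2 years post-randomization". The same sentence continues, in parentheses, "and scale by the number of patients with OUD; see Table Shell 6, Objective 1, Section 10.1". The next sentence spells out what is being divided: it warns that the intervention could affect both the "denominator (number of patients diagnosed with OUD) as well as the numerator (initiation and duration of treatment among treated patients", and concludes that "interpretation of these secondary analyses should be interpreted cautiously".

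The Objective 1 shells in SAP 10.1 say something else. Table 7, the shell for patients receiving OUD treatment during follow-up, is headed "Mean (SD) across clinics per 100 patients treated in the clinic post randomization". Supplementary Table 6, the number that 5.2.6 cites, is stratified by age, sex and race/ethnicity and is scaled per 10,000 patients in the subgroup.

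SAP 4.1 defines who counts as treated: "We do not require an OUD diagnosis for buprenorphine". It gives two reasons. Diagnoses were often missing in Phase 1, and PROUD clinics are expected to record them more fully, "so that requiring an OUD diagnosis could bias findings toward favoring the intervention clinics". Injectable naltrexone does need a diagnosis.

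**The concern.** An analyst following the text and one following Table 7 would report different quantities under the same name, and the cross-reference cannot settle the matter because it leads to a third table. The choice reaches several results: Table 7 has a P-value column and repeats the days-of-treatment outcome for the period when the nurse care manager was seeing patients and for the health systems that implemented successfully.

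Under the text's rule, numerator and denominator also cover different people. A patient on buprenorphine without an OUD code adds days but is not counted below the line. A patient with a code and no medication is counted below the line but adds no days. The result therefore moves with recognition, coding and initiation even when treated patients receive exactly the same number of days. A reader of a table about treated patients would naturally read it as days per treated patient.

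**Working it through.** The SAP gives no power, sample size or expected value for this analysis, so there is no planned figure to reproduce. Two checks apply.

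**1. How far do the two populations differ?** The inputs are from Protocol Table 2 (section 3.6.4): the sum of the two clinics' N, the percent with OUD, the percent on buprenorphine, and the percent with both (OUD in any year). Counts are N × percent / 100.

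| Site | N | OUD % | Bup % | Both % | Bup patients | Of these, coded |
|---|---|---|---|---|---|---|
| HF | 50,654 | 0.09 | 0.02 | 0.00 | 10.1 | 0 |
| HH | 29,042 | 0.03 | 0.01 | 0 | 2.9 | 0 |
| KPWA | 29,938 | 1.05 | 0.26 | 0.22 | 77.8 | 65.9 |
| MF | 24,073 | 0.29 | 0.08 | 0.02 | 19.3 | 4.8 |
| MC | 18,914 | 0.68 | 0.03 | 0.03 | 5.7 | 5.7 |
| UM | 20,545 | 0.09 | 0.01 | 0.00 | 2.1 | 0 |
| All | 173,166 | | | | 117.9 | 76.4 |

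- Share of buprenorphine patients with no OUD code: 1 − 76.4/117.9 = 35%. Using the three-year patient counts (287,420) instead gives 36%.
- OUD-diagnosed patients by the same method: about 586. Buprenorphine patients are 117.9/586 = 20% of that number.

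So the text's denominator would miss roughly a third of Phase 1 buprenorphine patients and would consist mostly of people who may not have been treated.

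**2. What does the text's rule do when treatment per patient is equal?** Let T be the number treated, d the days per treated patient, c the share of treated patients who are coded, and U the number coded but untreated. Then

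days / N diagnosed = d × T / (cT + U), whereas days / N treated = d.

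Set d = 200 in both arms. All inputs below are assumptions.

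| Scenario | UPC (T, c, U) | PROUD (T, c, U) | UPC | PROUD | Ratio |
|---|---|---|---|---|---|
| Coding differs, no untreated | 50, 0.7, 0 | 50, 1, 0 | 10,000/35 = 285.7 | 10,000/50 = 200.0 | 0.70 |
| Coding differs, 150 untreated | 50, 0.7, 150 | 50, 1, 150 | 10,000/185 = 54.1 | 10,000/200 = 50.0 | 0.925 |
| As above, and PROUD adds 100 untreated diagnoses | 50, 0.7, 150 | 50, 1, 250 | 54.1 | 10,000/300 = 33.3 | 0.62 |
| PROUD treats twice as many | 50, 0.7, 150 | 100, 1, 150 | 54.1 | 20,000/250 = 80.0 | 1.48 |
| PROUD moves 50 from untreated to treated | 50, 0.7, 150 | 100, 1, 100 | 54.1 | 20,000/200 = 100.0 | 1.85 |
| Five-fold more treated | 20, 0.7, 150 | 100, 1, 150 | 4,000/164 = 24.4 | 20,000/250 = 80.0 | 3.28 |

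With treated patients as the denominator, every row gives 200/200 = 1.00.

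**The case against.** **The intended denominator is obvious.** The section title, the population in its first clause and the Table 7 header all point to treated patients, and Shell 6 is plainly a misprint for Shell 7. Most of this stands, and it is why the repair is easy. But it is not a one-word slip: the following sentence restates the denominator as diagnosed patients and builds its caution on that.

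**The SAP already warns the reader.** It does say that the intervention may move both parts. It does not say that the two parts cover different people, or that the shell uses another denominator.

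**A reader might infer that the analysis is biased against PROUD.** Fuller coding in PROUD clinics, which 4.1 expects, does pull that way when nothing else changes. The documents do not support the unconditional claim. The trial's hypothesis is that PROUD raises initiation (Protocol 3.2.3.1), with a 5- to 10-fold rise in treatment days anticipated (Protocol 3.6.4), and higher initiation pushes the ratio up. The last three scenarios favour PROUD.

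**A reader might also take the Phase 1 ratios of diagnosed to buprenorphine patients as the size of a bias.** These are about 4.0 at KPWA (1.05/0.26), 3.6 at MF (0.29/0.08) and 23 at MC (0.68/0.03). They show that the two denominators differ in scale. A scale factor common to both arms cancels in the between-arm ratio. MC, with the largest factor, shows no uncoded buprenorphine patients at all (0.03/0.03).

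**The consequences are small.** This stands. The primary test is untouched. The SAP has other retention measures (80% of days, six months, discontinuation). Patient-level treatment days are also analysed among patients diagnosed before randomization, a sample that later coding cannot alter.

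**Conclusion.** The scaling rule in 5.2.6 is wrong as written. It contradicts the shell for the same analysis, cites an unrelated shell, and pairs treated patients' days with a count of diagnosed patients although buprenorphine needs no diagnosis. The result can differ between arms while days per treated patient are identical, and its net direction is not fixed: 0.62 to 3.28 in the scenarios shown.

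That range illustrates the mechanism and does not forecast the trial, because the treated counts, coding shares and untreated counts are all assumed. The 35% figure comes from Phase 1 percentages rounded to two decimals and not split by arm. At MF, for example, the coded share of 0.02/0.08 could lie between 0.015/0.085 = 18% and 0.025/0.075 = 33%. The figure shows that uncoded treatment is common enough to matter, but it does not estimate differential coding after randomization. The impact is limited to a secondary analysis.

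**What to change.** In SAP 5.2.6:

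- Scale by the number of patients with documented OUD treatment post-randomization, as in Objective 1 Table 7.
- Change the shell reference from 6 to 7.
- Reword the caution to say that the number and mix of treated patients may be affected by the intervention. A treated denominator removes the mismatch between populations, but the treated group is still defined after randomization.

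If a rate per OUD-diagnosed patient is also wanted, define it as a separate measure with numerator and denominator both limited to diagnosed patients.

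The main change costs a few words of SAP text. It needs no new data and no programming beyond the shell already planned.

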### 5.3 Primary Analytic Method for Objective 2 Primary Effectiveness Outcome Measure

Our primary outcome for the main Objective 2 (effectiveness) outcome is a patient-level measure of the number of days of acute care utilization over the follow-up period, which is a 2-year period for 5 of the 6 HCSs, and a 1.5-year period for the 6th HCS.

The primary analysis will be among individuals with an eligible PC visit pre-randomization who had an OUD diagnosis during the pre-randomization period (see definition of “Objective 2 primary study sample” in Section 3). The patient-level analysis will follow ITT principles, with patients analyzed according to the randomization group of the clinic to which they were assigned pre-randomization, regardless of the degree to which the clinic actually implemented the intervention, and regardless of whether the patient was actually treated by the NCM or seen post randomization.

We hypothesize that, among patients who had an eligible PC visit and were identified as having an OUD diagnosis pre-randomization (documented in their EHRs up to 3 years prior to randomization), individuals from a PROUD intervention clinic will have decreased acute care utilization after randomization as compared to individuals from a UPC clinic. We plan to fit a mixed-effect Poisson regression model (with log link) at the patient level to the number of days of acute care utilization. The model will account for clustering of patients within a clinic by including clinic-specific random intercepts. Specifically, the regression model will be of the following form:

$$\log[E(y_{ijk})] = \log(\text{days}_j) + \alpha + \beta * trt_{ij} + \gamma * z_{ijk} + \theta_{ij}$$

where

- $y_{ijk}$  is the observed number of days of acute care utilization of patient  $k$  in clinic  $i$  of HCS  $j$  over the follow-up period
- $trt_{ij}$  is the treatment indicator (PROUD intervention) for clinic  $i$  in HCS  $j$
- $z_{ijk}$  is the baseline value of the outcome during the two years prior to randomization for patient  $k$  in clinic  $i$  of HCS  $j$  ( $\gamma$  is the corresponding coefficient)
- $\theta_{ij}$  is the random effect for clinic  $i$  in HCS  $j$

Because one of the HCSs was randomized at a later date than the others, not all HCSs have the same amount of follow-up time. To account for this difference, we will include in the model an offset term for the number of days of potential follow-up time (e.g., 2 years for 5 of the HCSs and 1.5 years for the 6th HCS); in the above model,  $\log(\text{days}_j)$  denotes the offset term where  $\text{days}_j$  denotes the days of follow up in HCS  $j$ .

We will evaluate our primary Objective 2 hypothesis by testing the null hypothesis  $H_0: \beta = 0$  versus the two-sided alternative hypothesis that  $\beta$  is non-zero with a type 1 error rate of 0.05. In cluster-randomized trials with a small number of clusters, a small-sample correction is often necessary to obtain correct type 1 error rates. Although small-sample degree of freedom (DF) correction methods have been evaluated for continuous and binary outcomes under generalized linear mixed-effect models (GLMMs), there has not been prior guidance of which approach to use in our setting with a count outcome and covariate adjustment. Given this lack of knowledge, members of the PROUD statistical team are conducting simulations to evaluate alternate small-sample DF methods in this setting. Our results so far suggest that the optimal choice of testing procedure varies depending on the data-generating scenario in terms of the intraclass correlation

coefficient (ICC), number of clusters, and sample size within a cluster; however, using the likelihood ratio test with the Between-Within (BW) DF correction method (also referred to as “inner-outer” approach) appears to perform generally well in the scenario that aligned most closely with PROUD Phase 1 data used in the power simulation (see Appendix C).

Inclusion of a HCS-specific random effect. The above model accounts for clustering of patients within clinics but does not account for the possibility of additional correlation of outcomes from patients within the same HCS beyond any within-clinic correlation. The reason for this is because analyses of Phase 1 data suggested that within-clinic correlation was considerably larger than within-HCS correlation (the random-effect variance was 0.00016 for HCS versus 0.055 for clinic from a model including random effects for both). Although including a random-effect term that is not truly needed should not impact parameter estimates, including a HCS-level random effect leads to inferential challenges. In particular, as above there has not been guidance on applying small-sample DF correction methods when there are random-effects at two levels (here 12 clinics nested within 6 HCSs). We therefore chose the clustering level that explained most of the correlation for primary Objective 2 analyses. As a sensitivity analysis, we plan to examine the impact of additionally including a HCS-level random effect on the treatment effect parameter and standard error estimate.

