3.6.4 Phase 1 Impact on Design Considerations

Based on low rates of OUD diagnosis and treatment in Phase 1 of PROUD, and findings in MA that each NCM can treat 100-125 patients and that retention is 50-67% at 1 year, we anticipate at least a 5-10 fold increase in the number of patient days of OUD treatment if each PROUD intervention clinic compared to control. Phase 1 also led to several changes in the protocol of the PROUD trial. We summarize these changes here.

Table 2. The 6 PROUD Phase 1 Sites Able to Participate in the PROUD Trial (2016)

	HF	HH	KPWA	MF	MC	UM
Total N seen in 3 years	86,262	60,463	46,214	34,763	27,031	32,687
% Medicare	25.86	3.13	21.35	0	19.57	16.31
% State subsidized	9.67	75.98	6.46	0	23.35	4.90
% Uninsured	1.21	0	6.59	0	0	0.06
% 16-25 years old	15.87	9.05	14.71	19.13	15.61	8.55
% African American	33.65	22.31	5.75	37.36	9.56	14.67
% Hispanic	3.19	55.59	6.93	74.57	4.55	49.76
% OUD	0.09	0.03	1.05	0.29	0.68	0.09
% buprenorphine	0.02	0.01	0.26	0.08	0.03	0.01
% OUD (any yr) + bup.	0.00	0	0.22	0.02	0.03	0.00
% Methadone OTP	0	0	0.10	0	0.01	0
% Urgent care	1.90	0	18.03	10.64	25.72	0
% any ED	20.07	14.73	13.60	23.65	23.54	10.01
% any hospitalization	2.90	5.99	7.26	9.20	8.12	4.85
% any acute care	21.86	18.59	29.99	31.81	43.39	13.39
% with OUD	0.04	0.02	0.67	0.22	0.57	0.06
% without OUD	21.82	18.57	29.32	31.59	42.82	13.33
N in clinic #1	34,114	11,390	14,271	15,222	9,776	9,018
N in clinic #2	16,540	17,652	15,667	8,851	9,138	11,527
% overlap: 2 clinics	0.33 – 0.46	0.11-0.27	0.13 – 0.15	0.28 – 0.43	0.01 – 0.04	0.23-0.29
% seen 2016 & in 2014-2015	64.0-67.8	60.7 – 64.7	76.3-77.1	73.9-81.4	75.0-88.2	60.3 – 63.3

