### 5.7.2 Objective 2 Primary Effectiveness Outcome

We plan to conduct analyses of subgroups based on: age ( $< 26$  vs older) at randomization; sex; race and ethnicity (Hispanic, Non-Hispanic White, Non-Hispanic Black, Non-Hispanic Asian, Other), using similar subgroups as Objective 1. If one of the subgroups is small (fewer than 5% of patients in the sample), we will consider excluding that category or combining with the “Other” category. To examine whether the treatment effect may differ across groups, we plan to apply the same analytic approach as for the primary analysis of the Objective 2 outcome, in which we will additionally include an interaction term between the categorical subgroup variable of interest and the treatment effect term. As above, such comparisons are expected to be underpowered and will be interpreted cautiously. To aid in the interpretation of potential subgroup-specific effects, we plan to additionally conduct analyses of these subgroups for the patient-level treatment outcome of number of days of OUD medication treatment.

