## 6.2 Power Simulations for Primary Objective 2 Outcome

### 6.2.1 Description of Power Simulation

We investigated the power of the primary Objective 2 analysis via Monte Carlo simulation. We assumed the following sample sizes for the number of patients with a prior OUD diagnosis over a 3-year period from the Phase 1 data, reflecting the 3-year baseline period of PROUD during which patients with an OUD diagnosis will be identified:

site_id	clin_num	Clin	nOUD
A	1	A1	9
A	2	A2	12
C	1	C1	63
C	2	C2	39
E	1	E1	58
E	2	E2	200
I	1	I1	100
I	2	I2	49
J	1	J1	27
J	2	J2	10
K	1	K1	388
K	2	K2	290

We generated individual-level outcome data within each of the 12 clinics as follows. First, we randomly assigned one of the two clinics within a HCS to receive the PROUD intervention and the other to the Usual Primary Care (UPC) group. We then generated outcome data from a Poisson distribution with mean number of acute care days over a two-year period (time-frame of PROUD outcome ascertainment) using the following mean model,

$$\log E(y_{ijk}) = \alpha + \beta * trt_{ij} + \theta_{ij}$$

where

- 1)  $y_{ijk}$  is the number of days of acute care utilization of patient  $k$  in clinic  $i$  of HCS  $j$
- 2)  $trt_{ij}$  is the treatment indicator (PROUD intervention versus UPC) for clinic  $i$  in HCS  $j$
- 3)  $\theta_{ij} \sim N(0, \tau^2)$  is the random effect for clinic  $i$  in HCS  $j$  ( $\tau$  is the standard deviation of the clinic-level random effect)

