**Figure 2: Objective 2 Power Across Different Effect Sizes**

Here 'Prej' denotes the proportion of Monte Carlo iterations for which the null hypothesis was rejected; each panel corresponds to a different value of the random-effect SD ( $\tau$ ). Based on using the BW degree of freedom correction approach, we estimated that we have >80% power to detect values of  $RR_{ITT} < 0.65$  when  $\tau = 0.23$ , corresponding to a 35% reduction in the acute care utilization rate among patients in a PROUD versus UPC clinic. Similarly, we have >80% power to detect values of  $RR_{ITT} < 0.80$  when  $\tau = 0.12$  and of  $RR_{ITT} < 0.55$  when  $\tau = 0.35$ .

We next provide additional context on the corresponding proportion of patients in PROUD intervention clinics who would need to be treated for OUDs ( $p_{treat}$ ) in order to detect the above values of  $RR_{ITT}$  when the underlying relative risk of acute care utilization comparing patients treated for OUDs versus those who are not treated ( $RR_{treated}$ ) is 0.1 or 0.2.

	$\tau$	$RR_{ITT}$	Proportion of patients needing to be treated for OUD ( $p_{treat}$ )	
			RR among treated ( $RR_{treated}$ )=	
			0.1	0.2
Sensitivity	0.12	< 0.80	>22%	>25%
Primary	0.23	< 0.65	>39%	>44%
Sensitivity	0.35	< 0.55	>50%	>56%

Thus, under our primary assumption for the random-effect SD ( $\tau$ ) if at least 39-44% of patients with OUD in the PROUD intervention arm at baseline are treated for OUD by the NCM, then we will have over 80% power to detect at least a 35% decrease in acute care utilization ( $RR_{ITT} < 0.65$ )

comparing patients with OUD in the PROUD intervention arm versus UPC, when the true RR comparing treated to untreated patients with OUD ( $RR_{treated}$ ) is 0.1-0.2. If fewer patients are treated, then our power would be less than 80% under these same assumptions.

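### Objective 2 Poisson mixed model has no patient-level dispersion term: within-clinic treatment tests are anti-conservative, and the stated power is not established for the planned test

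*SAP*

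**What the plan says.** SAP 5.3 sets out the Objective 2 analysis of days of acute care: "We plan to fit a mixed-effect Poisson regression model (with log link) at the patient level". The terms are a follow-up offset, the arm, the patient's baseline value of the outcome and a clinic random intercept. The test is two-sided and asks whether β "is non-zero with a type 1 error rate of 0.05". Appendix C selects a likelihood ratio test with between-within degrees of freedom (LRT with BW2).

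The same model family is used elsewhere. For subgroups, SAP 5.7.2 will "additionally include an interaction term between the categorical subgroup variable of interest and the treatment effect term". SAP 5.5.3 adds a period-by-arm term and a composite likelihood ratio test. SAP 5.6 applies the approach to the other patient-level outcomes.

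The power run in SAP 6.2.1 uses Poisson data too: "We then generated outcome data from a Poisson distribution with mean number of acute care days over a two-year period". From it, SAP 6.2.2 reports: "we estimated that we have >80% power to detect values of" the intention-to-treat relative risk below 0.65 when the clinic SD τ is 0.23. That result is for the BW Wald F test without the baseline covariate. The Appendix C results shown come from a fitted model that matches the data-generating model.

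I found no dispersion check, negative-binomial or quasi-Poisson model, patient-level random effect or robust standard error in either document.

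**The concern.** Given the clinic effect and covariates, the model forces the variance of a patient's count to equal its mean. The outcome adds inpatient days to emergency and urgent-care days. One admission contributes several days at once, and some patients contribute none, so the variance should be well above the mean.

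The clinic intercept can absorb the excess for comparisons between clinics. It cannot do so for contrasts estimated among patients of the same clinic, such as arm by sex. There the standard error stays at its Poisson value and the p-value is too small. At stake are the reported interaction and omnibus p-values for Objective 2, and the power quoted for a secondary aim that the SAP describes as powered.

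**Working it through.** **Inputs.** SAP 6.2.1: 12 clinics with 9, 12, 63, 39, 58, 200, 100, 49, 27, 10, 388 and 290 OUD patients (total 1,245); 4.0 visits × 2.04 days = 8.16 days per 2 years; τ = 0.23; 10 denominator df. SAP Appendix C: Phase 1 ICC about 0.02. Protocol Table 2: 2016 percentages. Write φ for the variance/mean ratio of patient counts within a clinic; Poisson means φ = 1.

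**Reproducing the plan's figures** (2,000 repetitions, BW Wald, Poisson data). Type I error is 0.075, 0.066 and 0.064 at τ = 0.12, 0.23 and 0.35; the SAP gives 0.075, 0.070 and 0.067. Power is 81.1% (τ 0.12, RR 0.80), 85.5% (0.23, 0.65) and 80.0% (0.35, 0.55); the SAP states >80%. The figures reproduce.

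**Do the documents' numbers fit Poisson counts?**

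1. *Multi-day visits.* If visits were Poisson with L days each, φ = E[L²]/E[L] ≥ E[L] = 2.04.
2. *ICC.* With log-normal clinic effects, between-clinic variance = 8.16² × e^0.0529 × (e^0.0529 − 1) ≈ 3.81. Poisson within-clinic variance = 8.16 × e^0.02645 ≈ 8.38. ICC = 3.81/(3.81 + 8.38) ≈ 0.31, or 0.18 for visits with mean 4.0. An ICC of 0.02 at τ = 0.23 needs φ = 3.81 × 49/8.38 ≈ 22 on days, or about 11 on visits.
3. *Zeros.* OUD patients with no acute care: KPWA 1 − 0.67/1.05 = 36%; MC 1 − 0.57/0.68 = 16%. Poisson at 8.16/2 = 4.08 days per year predicts e^−4.08 = 1.7%. The smaller sites' ratios are too coarsely rounded to rely on: HF's 0.04/0.09 is compatible with 37% to 53% having any acute care, and HH's 0.02/0.03 with 43% to 100%.

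**Primary test of β.** With over-dispersed data the fitted clinic SD rises from 0.20 to 0.26-0.33 and absorbs the excess. Type I error, taking 0.23 as the pure clinic SD, is 0.048-0.060 for BW Wald and 0.028-0.038 for the LRT against F(1,10).

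**Arm-by-subgroup interaction.** The model's standard error is too small by √φ, so type I error ≈ 2[1 − Φ(1.96/√φ)]. Simulation used a 50% subgroup, no baseline covariate and 4,000 repetitions:

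| φ | Formula | Simulated |
|---|---|---|
| 1 | 5.0% | 4.5% |
| 2.04 | 17.0% | 16.3% |
| 5 | 38.1% | 39.4% |
| 10.4 | 54.3% | 55.8% |
| 22.3 | 67.8% | 68.1% |

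With negative-binomial data of shape 1.25 to 0.45 (φ = 1 + 8.16/1.25 = 7.5 to 1 + 8.16/0.45 = 19.1; 400 repetitions), the Poisson mixed model gave 49-64% and a negative-binomial mixed model 4.5-6%.

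**Power at RR 0.65, without baseline adjustment.**

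| Data | BW Wald | LRT, F(1,10) |
|---|---|---|
| Poisson, τ 0.23 | 85.5% | 79.6% |
| τ 0.23 is pure clinic SD, φ 10.9 | 65.0% | 56% |
| τ 0.23 is pure clinic SD, φ 22.3 | 50.5% | 43% |
| True τ 0.16, φ 10.4 (ICC 0.020; Poisson fit returns about 0.23) | 79.9% | 72% |

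The negative-binomial runs with τ 0.23 gave 79% for the LRT on Poisson data, 50-64% on over-dispersed data under the planned model, and 60-67% under a negative-binomial model. With baseline adjustment, assuming log-normal frailty correlated 0.5 between periods, LRT power was 71% (τ 0.23, φ 10.9), 53% (0.23, 22.3) and 84% (0.16, 10.4).

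**The case against.** The strongest reply is that the powered hypothesis is safe: β is a between-clinic contrast and its size holds. A reader might infer that the primary Objective 2 test is invalid; the simulations show otherwise.

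A reader might also infer that the >80% power is not delivered. The documents do not support that. The figure reproduces for the test it describes. The SAP does not say how τ = 0.23 was estimated, beyond a Phase 1 model with a clinic variance of 0.055 (√0.055 = 0.23). If that was a Poisson mixed model, τ already contains much of the patient-level variation and adding more would count it twice. The SAP also shows τ = 0.35, beyond the inflated fitted values of 0.26-0.33. The planned model includes a baseline covariate that the power run omits. About six points of the gap between 85.5% and 79.6% come from the change of test alone.

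The degree of over-dispersion is uncertain. One length of stay from one system is applied everywhere, and some zeros may be care received outside the system. Baseline utilisation could capture part of the patient variation: in a 300-repetition check with clinic fixed effects and shape 1.25, linear adjustment lowered the interaction error from 53% to 34%. At shape 0.45 it did not help (72%).

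Finally, the affected analyses are secondary. SAP 5.7.2 calls subgroup comparisons underpowered and promises caution; SAP 5.5.3 is labelled exploratory; several other outcomes are binary or categorical.

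These replies limit the point without removing it. A warning of low power prepares readers for false negatives, whereas the fault here is false positives. SAP 5.5.2 says the secondary-sample analysis cannot adjust for baseline utilisation in patients new to the system, so the partial relief from baseline adjustment is absent from 5.5.3.

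**Conclusion.** The concern holds for within-clinic treatment contrasts and for the status of the power statement. Severity: should-fix.

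- The arm-by-subgroup test has type I error of roughly 16% to 68% without baseline adjustment, for φ from 2.04 to 22.3. A reader might take about half the time as the error rate; that is one point in the range, and no single figure is supported.
- The period-by-arm term and composite test in 5.5.3 rest on the same likelihood. They were not simulated, so no rate is claimed for them.
- The primary test of β keeps near-nominal or conservative size.
- Power above 80% at RR below 0.65 is not established for the planned LRT-BW2. Unadjusted, it is about 79-80% on Poisson data, about 72% if τ = 0.23 already absorbs over-dispersion, and about 43-64% if it does not. Baseline adjustment may recover part of the loss.

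Assumptions: gamma patient frailty (log-normal in the adjusted runs); 10 df for the LRT; two years of follow-up in every system, although one has 1.5; Table 2 read as 2016 shares of all patients, with the planning mean applying to each site. The ICC may refer to visits or days. Monte Carlo error is about 1 point for power at 2,000 repetitions and about 2.5 points in the 400-repetition runs.

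**What to change.** In SAP 5.3, 5.5.3, 5.7.2 and the count outcomes of 5.6, use a negative-binomial mixed model or add a patient-level random intercept. Keep the log link, offset, clinic intercept and BW2 test, and retain Poisson as a sensitivity analysis.

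In 6.2, state how τ = 0.23 was estimated. Rerun 6.2 and Appendix C with over-dispersed counts under LRT-BW2, including the baseline covariate, and restate the power figure.

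The cost is SAP wording and simulation time; no new data are needed. The downsides are a possibly less favourable stated power and a small convergence risk. The model change should not be presented as restoring 80% power: its main gain is valid within-clinic inference.
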